## Descriptive Evaluation Analysis Plan

### The Evaluation of the Family Champions Project in Dallas, TX

#### A. Description of the intended intervention(s)

Anthem Strong Families' Family Champions Project (FCP) offers skill-building primary curriculum and support services to program participants. The evidence-based TYRO Leadership and TYRO Core Communication curricula, totaling 18 hours, are offered as group classes by trained facilitators in which low-income adults learn skills related to healthy relationships and financial wellbeing. Support services, including case management and additional, optional classes through Anthem's Mini-Clinic series, are available to all FCP participants.

The main intervention being tested in this descriptive evaluation is the multistep continuous quality improvement (CQI) cycle created by Midwest Evaluation and Research (MER) that aims to improve FCP program implementation. The content and components of each step in the process are described below.

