CQI Process Step 4	Assessing the results of targeted interventions that were put in place at specific sites based on the findings of the Step 2 and Step 3 reports	Reports are prepared annually in the fourth quarter of each grant year and discussed at standing CQI team meetings	Existing CQI team meetings are used to present and discuss Step 4 report findings (e.g., did the targeted metrics improve after implementing interventions? Does the metric now meet relevant standards? Were there any challenges with the implementation of interventions? How did frontline staff, leadership, and facility staff find the intervention? ); the evaluation lead facilitates the CQI team meetings and presents the Step 4 reports to the CQI team. Program leadership share Step 4 report findings with frontline staff in staff meetings.	CQI team members (program director, program manager, evaluation lead, data manager(s)); program staff (case managers, facilitators, recruitment and retention specialists) who are able to 1) provide feedback on challenges and successes with the implementation of the intended intervention, 2) see the results of the intervention
Relationship skills workshops	Healthy relationships curriculum (TYRO Core Communication; TYRO Leadership)	A total of 18 hours, with six two-hour sessions occurring weekly (TYRO Leadership) plus two three-hour sessions occurring weekly (TYRO Core Communication)	Group lessons provided online via Zoom or in-person at service sites; two trained facilitators lead every session	Individuals in the greater Dallas-Fort Worth area with low income

**Table 2.** Staff education and training (initial and ongoing)

Component	Education and initial training	Ongoing training
Relationship skills workshop	All facilitators, case managers, intake specialists, and other members of the staff must complete the workshop as a participant before entering the certified TYRO Facilitator training component. Once the training is complete, each facilitator observes an experienced staff	Facilitators complete an annual refresher process to ensure curriculum fidelity. That process includes observations by the Program Manager, Program Director, or another qualified designee. We attempt to provide opportunities to become re-certified every two to three years. Other

Component	Education and initial training	Ongoing training

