### 1. Research questions

RQ1.1: Did the multistep CQI process support changes in primary workshop dosage, program attrition rates, or survey response rates at the program level?

RQ2: Did meaningful improvements in primary workshop dosage, survey response rates, or program attrition rates vary by service site *for sites that focused on improving the same metrics?*

RQ3 [secondary]: Do participants report healthier partner relationship attitude outcomes after program participation, as compared to baseline?

RQ4 [secondary]: Was level of dosage associated with reporting healthier partner relationship attitude outcomes after program participation, as compared to baseline?

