### 2. Outcomes evaluation enrollment

This study was initially approved by Solutions IRB on 03/29/2021 and has been annually reviewed and approved on 03/15/2022, 03/07/2023, and 3/11/2024. Additionally, revisions to the study were submitted as amendments and were approved on 05/17/2022, 02/15/2023, and 08/29/2023.

Participants for the program, and thus the study, are recruited primarily from community partnerships, walk-ins to Anthem Strong Families, radio and social media advertising, and word of mouth referrals.

Program service locations have varied throughout the implementation of the program but have included:

---

- Schools
  - Stephen C. Foster Elementary School
  - Herbert Marcus Elementary School
  - Burnet Elementary School
- Treatment Centers / Transitional Facilities
  - Soul's Harbor Treatment Center
  - Free Man House Transitional Living Facility
  - Shurrun's House Sober Living Facility
  - Gateway Foundation Treatment Center
- Vickery Meadow Youth Development Foundation
- Buckner Children and Family Services, Family Hope Center at Bachman Lake
- Virtual services provided via Zoom

The projected enrollment and desired sample size for the study is 800 participants. The final report will include a breakdown of the number of sites, number of staff at each site, and number of participants at each site.

To be eligible for the program, and thus the study, participants must be 1) low-income individuals, 2) at least 18 years of age, 3) with no open criminal cases (can be deferred), and 4) able to speak and understand English or Spanish.

Consent for enrollment into the evaluation happens during program orientation, prior to the start of the first primary workshop. A consent form is provided to participants, and a script is read by either the facilitator or the data manager, explaining the study activities and the potential risks and benefits. Participants sign and date the consent form and return it to the data manager, who logs the record in a consent spreadsheet on MER's secure Dropbox.

Enrollment into the study began April 22, 2021 and is estimated to conclude February 15, 2025.

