### **3. Data sources and data collection**

The data source for the program implementation and performance outcome measures is nFORM administrative data. Program staff are responsible for entering and updating client and workshop information, including workshop attendance and current client status, on an ongoing basis. These data are summarized bi-weekly in Step 1 CQI reports with metrics at the program level and annually in Step 2-4 CQI reports with metrics at the site level to monitor trends in program enrollment, workshop dosage, program attrition rates, and survey response rates.

The data source for participant outcomes related to healthy partner relationship attitudes is the nFORM

Healthy Marriage Adult Program survey, administered at orientation before the first primary workshop (entrance survey) and at the final primary workshop session (exit survey).

**Table 3.** Sources of data to address the research questions

Data source	Timing of data collection	Mode of data collection	Start and end date of data collection
nFORM administrative data	Ongoing	Program staff enter and update data related to enrollment, attendance, and client status	Start: April 2021 End: April 2025
nFORM Healthy Marriage Adult Program Survey	At orientation before the first primary workshop (entrance survey) and at the end of the final primary workshop session (exit survey)	Online via tablet or on paper as necessary	Start: April 2021 End: April 2025

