**Family Champions Project
Statistical Analysis Plan**

Clinicaltrials.gov ID: NCT05298345

September 4, 2024

Analysis approach

To assess the association between the multistep CQI process and the outcome measures, trends in dosage, retention, and survey response rates will be assessed over time since the start of the program. If the CQI process has been effective in identifying and addressing issues that require intervention, we would expect that program implementation would get stronger over time, as measured by progress toward meeting programmatic targets for these measures.

Analytic sample

The analytic sample for RQ1 and RQ2 is made up of the participants who received services at the facilities that received CQI intervention efforts as part of the multistep CQI process. The aggregated dosage, retention, and survey response rate data for these participants will make up the analytic sample.

The analytic sample for the secondary research questions (RQ3 and RQ4) about participant healthy partner relationship attitudes will be defined as participants who have complete baseline and outcome data for the constructed outcome measure (complete case). Because these relationship questions are only shown to participants who report currently being in a romantic relationship, participants can only have complete case survey data if they report being in a relationship at both waves of data collection. As mentioned above, participants will only be included in the analytic sample if they have one or no missing values for the five items used to construct this outcome measure (80% or 100% of non-missing items). Participants who do not meet this threshold will have their outcome value assigned to missing and will not be included in the analytic sample; no imputation is planned for the outcome data.

Data preparation

Program-level and participant-level data will be downloaded as an Excel file using nFORM's data export feature. The data sets will be cleaned and prepared for analysis using the R Studio statistical software package. All files will be exported into R and cleaned separately before data sets are merged into a final, wide format file for analyses using nFORM client ID as the unique identifier for matching programmatic (dosage, client status, survey response rates) and participant survey data.

Analytic approach

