The analysis for this evaluation will be completed using Excel and the R Studio statistical software package. Trends in programmatic outcome measures will be assessed descriptively over time using graphs that show average dosage, attrition, and survey response rates by month since program start among participants who enrolled in that month. Trends in program-level (cross-site) averages will be assessed for improvements over time, and trends in site-level averages will be assessed both for improvements since program start and immediately following the implementation of targeted interventions, which will be noted on the graphs. Site-level averages will be compared across the full study time period. Assuming the continuous, rapid cycle learning and intervention of the multistep CQI process is happening as planned, average metrics are expected to improve over time and immediately following interventions.

For the secondary research question 3 analysis, a change score will be calculated for each complete case respondent using their average at program entry and their average at program exit. We will use paired sample

t-tests to assess the magnitude and significance of mean score changes among program participants in the analytic sample. For the secondary research question 4 analysis, a basic regression model will be used to determine if higher dosage of primary workshop hours is associated with higher average scores on attitudinal items. Findings are considered statistically significant based on a $p < 0.05$, two-tailed test.

Attrition

Sample attrition is not a concern for the programmatic measures assessed for RQ1 and RQ2.

For the secondary research questions, sample attrition is related to program retention, as participants can only have complete case data if they stay in the program to take their nFORM exit survey. Anthem Strong Families staff have implemented numerous strategies to increase participant retention. Retention is tracked on an ongoing basis as part of the bi-weekly CQI team meetings between Anthem and MER staff, so decreases in survey response rates or participant retention can be tracked and addressed in real time as cohorts are enrolled in the program.

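### The RQ3 paired t-test ignores clustering by workshop group, so its type I error exceeds 5% if change scores correlate within groups and the conclusion is meant to reach beyond the groups delivered.

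*SAP*

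**What the plan says.** The SAP (Analytic approach) computes one entry-to-exit change score per complete-case respondent for RQ3 and applies paired-sample "t-tests to assess the magnitude and significance of mean score changes among program participants in the analytic sample". A result is significant at two-tailed p < 0.05. The question, in Protocol section B.1, is "Do participants report healthier partner relationship attitude outcomes after program participation, as compared to baseline"; it is labelled secondary.

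The program is delivered in groups. The Protocol's description of the intervention says the two curricula "are offered as group classes by trained facilitators", and Table 1 adds: "Group lessons provided online via Zoom or in-person at service sites; two trained facilitators lead every session". The SAP's Attrition paragraph refers to problems being "addressed in real time as cohorts are enrolled in the program".

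Neither document mentions clustering, an ICC, a random effect, cluster-robust standard errors or a sensitivity analysis by group or site for RQ3. Neither gives the size of a workshop group or the expected number of RQ3 complete cases.

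**The concern.** A paired t-test removes the correlation between a person's two surveys. It still assumes that the change scores of different people are independent. People in the same workshop share facilitators, sessions and setting between the two surveys, so their changes may move together. Group differences that are equal at entry and exit cancel in the change score; differences that arise during the program do not.

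If the changes are positively correlated within groups, the reported standard error is too small for any conclusion about the program beyond the particular groups delivered. Chance differences between groups would then be declared a significant change more often than 5% of the time, and the confidence interval would be too narrow. What is at stake is the error rate and interval of one secondary test.

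**Working it through.** **Inputs from the documents.** Two-sided significance level 0.05 and an individual-level paired t-test (SAP, Analytic approach); delivery in groups (Protocol, description of the intervention and Table 1); 800 planned enrollees (Protocol B.2).

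**Inputs assumed, because the documents do not give them.** Analysed participants per workshop group, m = 3, 5 or 10. ICC of the change score within groups = 0 to 0.10.

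**Step 1: reproduce the plan's figure.** With independent change scores, type I error = 2 × (1 − Φ(1.96)) = 5.0%, as the SAP states.

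**Step 2: allow for clustering, equal groups.** The true variance of the mean change is DE = 1 + (m − 1) × ICC times the variance the t-test uses. The true standard error is √DE times the reported one, and the actual type I error is 2 × (1 − Φ(1.96/√DE)). For example, with m = 5 and ICC 0.05, DE = 1 + 4 × 0.05 = 1.20, √DE = 1.095, 1.96/1.095 = 1.79, and type I error is 7.4%.

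| Analysed per group | ICC 0.02: DE, type I error | ICC 0.05 | ICC 0.10 |
|---|---|---|---|
| 3 | 1.04, 5.5% | 1.10, 6.2% | 1.20, 7.4% |
| 5 | 1.08, 5.9% | 1.20, 7.4% | 1.40, 9.8% |
| 10 | 1.18, 7.1% | 1.45, 10.4% | 1.90, 15.5% |

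Over this range the true standard error is √1.04 = 1.02 to √1.90 = 1.38 times the reported one.

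**Step 3: check by simulation.** With a random group effect, equal groups, 200 or 400 analysed participants and 20,000 runs per setting, the ordinary t-test rejected as follows.

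- ICC 0: 4.8–5.0%.
- ICC 0.05: 7.3–7.4% (m = 5) and 10.4–10.8% (m = 10).
- ICC 0.10: 9.7–9.9% (m = 5) and 15.4–15.6% (m = 10).

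A t-test on group-mean changes gave 4.7–5.1% throughout.

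**Step 4: unequal groups.** Group sizes were drawn uniformly; 15, 30 or 60 groups; normal change scores; 10,000 runs per setting. Type I error of the ordinary t-test:

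| Group sizes (mean) | ICC 0.02 | ICC 0.05 | ICC 0.10 |
|---|---|---|---|
| 1–5 (3) | 5.6–5.8% | 6.4–6.6% | 7.9–8.4% |
| 2–8 (5) | 5.7–6.2% | 7.9–8.0% | 10.4–10.6% |
| 2–18 (10) | 7.4–8.3% | 11.7–12.0% | 18.1–18.4% |

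The excess is larger because large groups weigh more. The effective m is the mean squared size over the mean size: 11/3 = 3.7, 29/5 = 5.8 and 124/10 = 12.4. At ICC 0 the test stayed at 4.7–5.3%.

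**Step 5: how large must the ICC be?** A type I error of 7.5% needs DE = (1.960/1.780)² = 1.212, and 10% needs DE = (1.960/1.645)² = 1.420. With ICC = (DE − 1)/(m − 1) and equal groups:

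| Analysed per group | ICC for 7.5% | ICC for 10% |
|---|---|---|
| 3 | 0.106 | 0.21 |
| 5 | 0.053 | 0.105 |
| 10 | 0.024 | 0.047 |

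**The case against.** **Both conditions are unproven.** No document gives an ICC, and because pairing cancels stable group differences the ICC of the change may be near 0. This stands: the size of the error cannot be fixed from the documents. It does not justify assuming independence without comment. Workshop members share facilitators and sessions, sites range from schools to treatment centers to Zoom, and Protocol section 3 of the implementation study says CQI interventions are introduced at particular sites and with particular cohorts.

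**The plan may intend a conclusion about this program's own participants only.** It is called a descriptive evaluation, the main intervention tested is the CQI process, study eligibility equals program eligibility, and the RQ3 test is worded as concerning participants in the analytic sample. On that reading the delivered groups are fixed, the inflation does not arise, and the t-test is if anything conservative. The reading is possible. However, the wording names who is analysed and does not say where the conclusion stops, and the plan attaches a significance rule to the result.

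**The upper figures need large analysed groups.** Analysed members must stay to the exit survey and miss no more than one of the five items at each wave, and "participants can only have complete case survey data if they report being in a relationship at both waves of data collection". If 10 to 20 enroll per group (an assumption), ten analysed means that 50% to 100% of enrollees qualify. This stands; the rows for 3 and 5 per group are the more plausible ones.

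**Little depends on RQ3.** It is secondary, complete-case and uncontrolled, so a significant change could not be attributed to the program even with an exact 5% error. This also stands and limits the importance of the point.

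**Conclusion.** The concern holds as a conditional statement. The planned RQ3 test makes no allowance for workshop group. If the change-score ICC is positive and the conclusion is meant to reach beyond the groups delivered, the type I error is above the stated 5%.

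Under the assumed ranges it is 5.5% to 9.8% with 3 to 5 analysed per group and up to 15.5% with 10 (equal groups), and somewhat higher with unequal groups. With 3 to 5 per group and ICC 0.02 the excess is under 1 percentage point. If the ICC is 0, or the delivered groups are treated as fixed, the t-test does not exceed 5%.

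This should be corrected because the remedy is cheap, but it bears on one secondary test only. RQ1 and RQ2 are descriptive and unaffected. The RQ4 regression is not specified in enough detail to show a wrong variance method there.

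**What to change.** **Change to the SAP.** Keep a workshop-group identifier in the analysis file and estimate the RQ3 mean change from an intercept-only model of the change score, using one of the following:

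- (a) CR2 cluster-robust standard errors by workshop group, with Satterthwaite or groups-minus-1 degrees of freedom; or
- (b) a random intercept for workshop group, with Satterthwaite or Kenward-Roger degrees of freedom.

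Use a normal-theory test with neither. Report the 95% confidence interval, the ICC and the number of groups. If the conclusion is meant only for the groups delivered, say so in one sentence; the t-test may then stay. Use the same variance method for RQ4 once its model is specified.

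**Which option.** Option (a) is the better tested. Across 36 unequal-group settings (the three size ranges; 15, 30 or 60 groups; ICC 0 to 0.10), type I error was:

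| Method | Type I error |
|---|---|
| CR2, Satterthwaite df | 4.6–5.5% |
| CR2, groups minus 1 df | 4.8–5.8% |
| Random intercept, Satterthwaite df | 2.2–5.2% (conservative with few groups) |
| Random intercept, normal test | 4.1–7.1% |
| Uncorrected robust SE, normal test | 5.5–9.2% |

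Kenward-Roger was not simulated.

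**Cost.** SAP wording and a group identifier; no new data collection if group can be linked to client ID. The documents do not say whether the nFORM export carries a workshop-group field, but nFORM already records attendance by session (Protocol Table 4) and supplies data "annually in Step 2-4 CQI reports with metrics at the site level" (Protocol B.3). They also do not say whether a participant stays in one group across both curricula, so the SAP would need to define the group.

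Intervals become wider. If the ICC is 0, the CR2 interval with Satterthwaite df is about 1.5% wider with 60 groups, 3–4% with 30 and 8–9% with 15. The Protocol's enrollment figure ("The projected enrollment and desired sample size for the study is 800 participants") would give 800/20 = 40 to 800/10 = 80 groups at an assumed 10 to 20 enrolled per group.
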